#### 8.3.6. Follow-up of AEs and SAEs

After the initial AE/SAE report, the Investigator is required to proactively follow each participant at subsequent visits/contacts. All SAEs/MAAEs/AESIs/AEs leading to withdrawal will be followed until resolution, stabilization, the event is otherwise explained, or the participant is lost to follow-up (as defined in [Section 7.3](#)). Further information on follow-up procedures is provided below:

- The Investigator is obligated to perform or arrange for the conduct of supplemental measurements and/or evaluations as medically indicated or as requested by the Sponsor to elucidate the nature and/or causality of the AE or SAE as fully as possible. This may include additional laboratory tests or investigations, histopathological examinations, or consultation with other healthcare professionals.

- If a participant dies during participation in the study or during a recognized follow-up period, the Investigator will provide the Sponsor with a copy of any postmortem findings including histopathology (if available).
- New or updated information will be recorded in the originally submitted documents.
- The Investigator will submit any updated SAE data to the Sponsor within 24 hours of receipt of the information.

### **8.3.7. Reporting of SAEs/AESIs/SUSARs**

AESIs and SUSARs will be reported to the Sponsor in the same manner and time frame as SAEs.

#### **SAE Reporting to the Sponsor via an Electronic Data Collection Tool**

- The primary mechanism for reporting an SAE to the Sponsor will be the electronic data collection tool (ie, EDC).
- If the electronic system is unavailable, then the site will use the paper SAE data collection tool (see next section) to report the event within 24 hours of becoming aware of the event.
- The site will enter the SAE data into the electronic system as soon as it becomes available.
- After the study is completed at a given site, the electronic data collection tool will be taken offline to prevent the entry of new data or changes to existing data.
- If a site receives a report of a new SAE from a study participant or receives updated data on a previously reported SAE after the electronic data collection tool has been taken offline, then the site can report this information on a paper form (see next section).

#### **SAE Reporting to the Sponsor via Paper Data Collection Tool**

- If EDC is unavailable and the site needs to use a paper form to report SAEs, email transmission of the SAE paper data collection tool may be used to transmit this information to the Sponsor.
- Initial notification via email does not replace the need for the Investigator to complete and sign the electronic SAE data collection tool within the designated reporting timeframes.
- AE reports should be emailed to the email address provided in [Section 10.3.1](#).

### **8.3.8. Regulatory Reporting Requirements for SAEs**

- Prompt notification within 24 hours by the Investigator to the Sponsor of an SAE, including those considered to be a SUSAR, is essential so that legal obligations and ethical responsibilities towards the safety of participants and the safety of a study intervention under clinical investigation are met.
- The Sponsor has a legal responsibility to notify both the local regulatory authority and other regulatory agencies about the safety of a study intervention under clinical

investigation. The Sponsor will comply with country-specific regulatory requirements relating to safety reporting to the regulatory authority, IRBs/IECs, and Investigators. For example, for reports that are required to be submitted to the European Union (ICSRs), will be submitted via the EVCTM Gateway.

- An Investigator who receives an Investigator safety report describing an SAE or other specific safety information (eg, summary or listing of SAEs) from the Sponsor will review and then file it along with the IB and will notify the IRB/IEC, if appropriate according to local requirements.
- For expedited reporting purposes, the expectedness of SAEs will be assessed against the study treatment regimen the participant is receiving at the time of the event. AE terms not listed as expected events in the IB for study intervention will be considered unexpected.
- Investigator safety reports must be prepared for SUSARs according to local regulatory requirements and Sponsor policy and forwarded to Investigators as necessary.

### 8.3.9. **Pregnancy**

- Any participant who becomes pregnant while participating in the study may continue study participation.
- Details of all pregnancies in participants will be collected after the start of study intervention and until 28 days following the last injection. Participants who become pregnant at any time during the study should remain in the study and complete all study visits as scheduled.
- If a pregnancy is reported, the Investigator will record pregnancy information on the appropriate form and submit it to the Sponsor within 24 hours of learning of the participant's pregnancy (see [Section 10.3.2](#)).
- While pregnancy itself is not considered to be an AE or SAE, any pregnancy complication or elective termination of a pregnancy for medical reasons will be reported as an AE or SAE.
- Abnormal pregnancy outcomes (eg, spontaneous abortion, fetal death, stillbirth, congenital anomalies, ectopic pregnancy) are considered SAEs and will be reported as such (refer to [Section 8.3.7](#)).
- The participant will be followed to determine the outcome of the pregnancy. The Investigator will collect follow-up information on the participant and the neonate and the information will be forwarded to the Sponsor.
- Any poststudy pregnancy-related SAE considered reasonably related to the study intervention by the Investigator will be reported to the Sponsor as described in [Section 8.3.7](#). While the Investigator is not obligated to actively seek this information in former study participants, they may learn of an SAE through spontaneous reporting.

Prior to continuation of study intervention following pregnancy, the following must occur:

- The Sponsor and the relevant IRB/IEC give written approval.
- The participant gives signed informed consent.
- The Investigator agrees to monitor the outcome of the pregnancy and the status of the participant and their offspring.

#### **8.4. Pharmacokinetics**

Pharmacokinetics parameters are not evaluated in this study.

#### **8.5. Pharmacodynamics**

Pharmacodynamics parameters are not evaluated in this study.

#### **8.6. Future Genetics Research**

Future genetics research will not be performed.

#### **8.7. Biomarkers**

Blood samples for assessment of cTnI levels will be collected from all participants at the following timepoints, as specified in the SoA ([Table 1](#)) and as detailed in the Laboratory Manual provided separately to the study sites.

- Baseline Day 1 (before injection)
- Day 4 (3 days after Injection 1)
- Day 29 (before injection) (28 days after Injection 1)
- Day 32 (3 days after Injection 2)
- Day 57 (28 days after Injection 2)

Elevated cTnI values will be defined based on the sex-specific 99th percentile cutoff of the assay that will be used for the study.

The Sponsor may store samples for the time period specified in the ICF to achieve study objectives. Samples may be used for further research by the Sponsor or others such as universities or other companies to contribute to the understanding of cardiac or other diseases, the development of related or new treatments, or research methods, as specified in the ICF.

#### **8.8. Immunogenicity**

Not applicable.

#### **8.9. Health Economics**

Health economics are not evaluated in this study.

## 9. STATISTICAL CONSIDERATIONS

This section summarizes the planned statistical analysis strategy and procedures for the study. The details of the statistical analyses will be provided in the SAP, which will be finalized before the clinical database lock for the study and intervention unblinding. If, after the study has begun, but prior to any unblinding, changes are made to the primary and/or key secondary objectives/hypotheses, or the statistical methods related to those hypotheses, then the protocol will be amended (consistent with ICH E9). Changes to other secondary or exploratory analyses made after the protocol has been finalized, along with an explanation as to when and why they occurred, will be listed in the SAP or CSR for the study.

### 9.1. Blinding and Responsibility for Analyses

This study is observer blind. The Investigator, study staff, study participants, study site monitors, and Sponsor personnel (or its designees) will be blinded to the study intervention administered until study end.

The study Data Blinding Plan provides details of the blinding/unblinding process and personnel. The study site staff, Investigators, study monitors, and participants will remain blinded until the EOS.

### 9.2. Statistical Hypothesis

There is no hypothesis testing planned in this study. The proposed number of participants is considered sufficient to provide a descriptive analysis of the rates of cTnI elevations after study intervention.

### 9.3. Analysis Sets

The analysis sets are defined in [Table 5](#).

**Table 5: Analysis Sets**

Analysis Set	Description
Randomization Set	All randomized participants.
Safety Set	All randomized participants who receive at least one dose of study intervention. Participants will be included in the intervention group corresponding to Injection 1 or Injection 2 received.
Evaluable Set	All participants in the Safety Set who have no major protocol deviations or conditions/medications that impact critical or key analysis data.

### 9.4. Statistical Analyses

The SAP will be finalized before database lock and will describe the preplanned statistical analysis details/data derivations, the participant populations to be included in the analyses, and procedures for accounting for missing and/or unused data.

This section is a summary of the planned statistical analyses of the primary and secondary endpoints.

#### **9.4.1. Efficacy Analyses**

No efficacy endpoints are planned for this study.

#### **9.4.2. Safety Analyses**

All safety analyses will be based on the Safety Set.

Safety will include SAEs, MAAEs, AESIs, AEs leading to withdrawal, vital sign measurements, and physical examination findings.

The number and percentage of participants with SAEs, MAAEs, AESIs, and AEs leading to withdrawal will be summarized. These unsolicited AEs will be presented by MedDRA system organ class and preferred term. The unsolicited AEs will be coded according to the MedDRA Dictionary for Adverse Reaction Terminology.

The number of events of SAEs, MAAEs, AESIs, and AEs leading to withdrawal will be reported in summary tables accordingly using descriptive statistics. Pregnancy outcomes will also be summarized.

The safety summaries will be presented by study intervention and injection (ie, post-Injection 1 and pre-Injection 2, and post-Injection 2), and for participants who receive the mRNA-1273.712 for Injection 1 or Injection 2 (ie, post-mRNA-1273.712 injection and throughout the study).

#### **9.4.3. Biomarker Analyses**

##### **cTnI analysis**

All statistical analyses will be descriptive.

The primary analysis for the proportion of cTnI elevations will be performed in the ES. The following groups are defined for the analysis of cTnI:

- mRNA-1273.712 group: participants who receive mRNA-1273.712 for Injection 1 in the mRNA-1273.712 - placebo sequence (Sequence 1), and participants who receive mRNA-1273.712 for Injection 2 in the placebo - mRNA-1273.712 sequence (Sequence 2).
- placebo group: participants who received placebo for Injection 1 in the placebo - mRNA-1273.712 sequence (Sequence 2), and participants who receive placebo for Injection 2 in the mRNA-1273.712 - placebo sequence (Sequence 1).

A participant may be included in both mRNA-1273.712 group and placebo group according to Injection 1 and Injection 2 received for the analysis of cTnI.

The primary endpoint for the proportion of participants with elevated cTnI at Day 4 or Day 32 (3 days after Injection 1 or Injection 2) will be summarized for the mRNA-1273.712 group and placebo group in the ES.

The secondary endpoints of the proportion of participants with elevated cTnI at preinjection Day 1, and the proportion with elevated cTnI at Day 29 (28 days after Injection 1 and

pre-Injection 2) or Day 57 (28 days after Injection 2) will be summarized for the mRNA-1273.712 group and placebo group in the ES.

The proportion of participants with elevated cTnI at each timepoint (Day 1, Day 4, Day 29, Day 32, and Day 57) for mRNA-1273.712 group and placebo group will be summarized for mRNA-1273.712 group and placebo group, overall, by age group (12 through 17 and  $\geq 18$  through 30 years of age) and by sex.

The proportions of participants with elevated cTnI described above will be summarized using percentage and 95% CI with the Clopper-Pearson method. The 95% CI for the difference in proportions between mRNA-1273.712 group and placebo group will be calculated using the Miettinen and Nurminen method.

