Blood samples will be collected from participants on scheduled visits (at injection visits, samples will be collected prior to injection) as specified in the SoA ([Table 1](#)) for assessment of cTnI. To aid in interpretation of cTnI assessment, participants will record vigorous physical activities in an eDiary for specific periods during the study (ie, if an elevated cTnI level is detected during the analysis, the activity data for that participant will be reviewed for correlation of vigorous physical activities with elevated cTnI levels) ([Table 2](#)). Depending on when the study injections or EOS is scheduled to be completed, the participant must complete the eDiary for 4 consecutive days post-Injection 1 (Day 1), 4 consecutive days pre- and post-Injection 2 (Day 29), and 4 consecutive days prior to the EOS visit (Day 57), and on the day of the EOS visit. Participants will be encouraged, but not required, to avoid vigorous physical activities, when possible, for 4 days before and after each study injection.

- Note: Vigorous physical activities refer to activities that take hard physical effort and make you breathe much harder than normal.

The study will be comprised of 5 scheduled in-clinic visits including a combined Screening and Day 1 Visit. Procedures for Screening and injection/baseline should be performed on the same day (Day 1 Visit) but may be performed on 2 separate days if needed due to extenuating circumstances ([Section 1.3](#)). This study will be conducted in compliance with the protocol, GCP, and all applicable regulatory requirements.

Participants will be in the study for approximately 2 months, which includes up to 7 days for Screening and Baseline (Day -7 to Day 1), with administration of study injection on Day 1 and Day 29 and approximately 2 months of follow-up (28 days after each injection).

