#### **9.6. Sample Size Determination**

Approximately 1000 participants will be randomized in a 1:1 ratio to one of 2 intervention sequences (approximately 500 participants in each intervention sequence) in this study, to receive **[REDACTED]**  $\mu$ g of mRNA-1273.712 followed by placebo 28 days later (mRNA-1273.712 – placebo [Sequence 1]) or to receive placebo followed by **[REDACTED]**  $\mu$ g of mRNA-1273.712 28 days later (placebo – mRNA-1273.712 [Sequence 2]). Approximately 1000 participants will receive **[REDACTED]**  $\mu$ g of mRNA-1273.712 for Injection 1 or Injection 2, due to the crossover design. Assuming approximately 10% of participants would be excluded from the mRNA-1273.712 group (Injection 1 or Injection 2) in the ES due to any reasons (eg, early dropout, and major protocol deviations that impact key analysis data), the study has more than 90% probability to observe at

least 1 participant receiving mRNA-1273.712 (Injection 1 or Injection 2) with an elevated cTnI at a true rate of 0.3%.

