#### **6.3.1. cTnI Analysis**

Analyses will be performed by intervention group (mRNA-1273.712, placebo, and Total) and visit: Day 1 or Day 29 (Pre-Injection 1 or Pre-Injection 2), Day 4 or Day 32 (3 days after Injection 1 or Injection 2), and Day 29 or Day 57 (28 days after Injection 1 or Injection 2); and by intervention sequence (mRNA-1273.712 – placebo, placebo – mRNA-1273.712, and Total) and visit: Day 1 (pre-Injection 1), Day 4 (3 days after Injection 1), Day 29 (pre-Injection 2, 28 days after Injection 1), Day 32 (3 days after Injection 2), and Day 57 (28 days after Injection 2).

Percentages will be based on number of participants within each intervention group or sequence with non-missing cTnI data at each corresponding timepoint.

Statistics will include the number of participants (n), median, min, max, Q1, and Q3. The number of participants with elevated cTnI, or  $cTnI > \text{elevated cTnI threshold}$  by sex will be also presented, along with the percentages and 95% CI with the Clopper-Pearson method. Difference in percentages of participants with elevated cTnI levels between mRNA-1273.712 and placebo intervention groups, and the corresponding 95% CI will be calculated using the Miettinen and Nurminen method. Change in proportion of elevated cTnI levels from Day 1 (baseline) and/or from Day 29 for subsequent timepoints with the corresponding 95% CI using the adjusted Wald intervals will be measured. This change will be calculated as the difference between the proportion of participants with elevated cTnI at specified subsequent timepoint and the proportion of participants with elevated cTnI at Day 1 or Day 29. These analyses will apply to the primary, secondary, and exploratory endpoints. Additionally, participants with at least one non-missing cTnI data at day of injection, or 3 days after each injection will be summarized and categorized by normal, elevated, and missing values at each corresponding timepoint.

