## 7. Changes from Planned Analyses in Protocol

There are no changes from planned analyses in protocol.

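### The pooled vaccine-minus-placebo confidence interval treats the two groups as different people, although most participants are in both

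*Protocol*

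**What the plan says.** Protocol 9.4.3 defines the vaccine and placebo groups by the injection received, pooling both sequences, and states: "A participant may be included in both mRNA-1273.712 group and placebo group according to Injection 1 and Injection 2 received". For the comparison it specifies: "The 95% CI for the difference in proportions between mRNA-1273.712 group and placebo group will be calculated using the Miettinen and Nurminen method".

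SAP 6.3.1 analyses these groups at three pooled visits. One combines the samples taken four weeks after each injection (Days 29 and 57); the other two are written as "Day 1 or Day 29 (Pre-Injection 1 or Pre-Injection 2), Day 4 or Day 32 (3 days after Injection 1 or Injection 2". For the difference between groups, "the corresponding 95% CI will be calculated using the Miettinen and Nurminen method". The SAP also gives results by sequence and single visit, and changes in proportion from Day 1 or Day 29 with adjusted Wald intervals. Neither document plans a paired or clustered interval for vaccine against placebo. SAP 7 adds: "There are no changes from planned analyses in protocol".

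On numbers, Protocol 9.6 says "Approximately 1000 participants will be randomized in a 1:1 ratio to one of 2 intervention sequences" and assumes that "approximately 10% of participants would be excluded from the mRNA-1273.712 group".

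**The concern.** In a two-period crossover, each completer contributes one sample after vaccine and one after placebo. Miettinen-Nurminen uses only the two group totals and sample sizes, so it cannot tell whether the elevated people in the two groups are the same people. If some are, the two proportions are positively correlated and the true variance of their difference is smaller than the method assumes.

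Recurrence within a person is plausible but not established. Protocol 2.1 names strenuous exercise among the causes of raised cTnI, and Protocol 4.1 says "Participants will be encouraged, but not required, to avoid vigorous physical activities". Exclusion criteria 5 and 8 and Table 8 remove many chronic causes but not all.

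This is the only planned interval for the pooled vaccine-minus-placebo difference in the primary endpoint. An interval that is too wide cannot create a false signal, but it can include zero when the paired data exclude it. In a safety-biomarker study that is the less comfortable direction.

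**Working it through.** **The plan's own figure.** With 10% exclusion, 900 of 1000 remain in the vaccine group. P(at least 1 elevation at a rate of 0.3%) = 1 - 0.997^900 = 93.3%, which agrees with the stated more than 90%. This figure concerns one group and is not affected.

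**Overlap.** Protocol 9.6 gives 10% exclusion for the vaccine group only. Assuming 10% for placebo too, the smallest overlap is 1000 - 100 - 100 = 800. It is about 900 if the same participants are excluded from both groups, which is likely because the Evaluable Set is defined by participant. If placebo loses a share d, the minimum is 900 - 1000d: 850 at 5%, 750 at 15%.

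**Variance.** With n per group, m people in both, rate p and within-person correlation ρ:

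Var(difference) = 2p(1-p)/n - 2mρp(1-p)/n²

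The independent-sample formula drops the second term, so its standard error is too large by the factor 1/√(1 - mρ/n). For m = 800, n = 900 the factor is 1.00, 1.10, 1.34 and 1.86 at ρ = 0, 0.2, 0.5 and 0.8. The range of ρ is an assumption.

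**The two score statistics.** Let b be the number elevated after vaccine only and c after placebo only.

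- Miettinen-Nurminen (MN): (p̂₁ - p̂₂ - δ) / √{[p̃₁(1-p̃₁)/n₁ + p̃₂(1-p̃₂)/n₂] · N/(N-1)}, with N = n₁ + n₂ and p̃ the estimates constrained to a difference of δ.
- Tango: (b - c - nδ) / √{n[2q̃ + δ(1-δ)]}, with q̃ = [√(B²-4AC) - B]/(2A), A = 2n, B = -b - c + (2n - b + c)δ, C = -cδ(1-δ).

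Each 95% limit is the δ at which the statistic equals ±1.96.

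A hand check at δ = 0 for 9 versus 3 among 900 pairs: MN uses the pooled rate 12/1800 and gives 1.74 whatever the sharing. Tango reduces to (b - c)/√(b + c):

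- none shared: 6/√12 = 1.73
- 1 shared: 6/√10 = 1.90
- 2 shared: 6/√8 = 2.12
- 3 shared: 6/√6 = 2.45

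**Intervals (percentage points).**

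| Pairs | Elevated, vaccine vs placebo | Elevated both times | MN | Tango |
|---|---|---|---|---|
| 900 | 9 vs 3 | 0 | -0.10 to 1.60 | -0.10 to 1.60 |
| 900 | 9 vs 3 | 1 | -0.10 to 1.60 | -0.03 to 1.55 |
| 900 | 9 vs 3 | 2 | -0.10 to 1.60 | 0.07 to 1.50 |
| 900 | 9 vs 3 | 3 | -0.10 to 1.60 | 0.24 to 1.45 |
| 800 | 9 vs 3 | 0 | -0.11 to 1.79 | -0.12 to 1.79 |
| 800 | 9 vs 3 | 1 | -0.11 to 1.79 | -0.03 to 1.74 |
| 800 | 9 vs 3 | 2 | -0.11 to 1.79 | 0.08 to 1.69 |
| 800 | 9 vs 3 | 3 | -0.11 to 1.79 | 0.27 to 1.63 |
| 900 | 8 vs 2 | 1 | -0.02 to 1.55 | 0.07 to 1.50 |
| 900 | 3 vs 1 | 1 | -0.32 to 0.88 | -0.20 to 0.81 |

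The last row is near the planning rate: 0.3% of 900 is 2.7 elevations.

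**Simulated coverage.** 900 pairs, no true difference, 20,000 runs per scenario; true rates 0.3%, 0.5% and 1%.

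| Share of elevations recurring | MN coverage | Mean MN width / Tango width |
|---|---|---|
| none | 94.9% to 95.6% | 1.00 |
| a quarter | 97.6% to 97.7% | 1.08 to 1.12 |
| half | 99.3% to 99.4% | 1.19 to 1.31 |

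Tango covers 94.9% to 97.6% in the same scenarios. With only 800 shared of 900 per group, MN coverage is 97.3% to 97.4% at ρ = 0.25 and 99.1% at ρ = 0.5 (rates 0.3% and 1.0%).

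**The case against.** The strongest reply is that nothing turns on this interval. Protocol 9.2 plans no hypothesis test, 9.4.3 calls all analyses descriptive, and there is no margin or success rule. Elevations are expected to be rare. At 900 pairs, with up to 9 vaccine elevations and at least as many as after placebo, the two methods never disagree about zero when there are 4 or fewer vaccine elevations. The first disagreement is 5 versus 1 with the one placebo elevation shared, and every disagreement needs at least half of the placebo elevations to recur after vaccine. Known causes are excluded, and the documents expect elevations to last from days to a couple of weeks, against 28 days between injections. All this stands and limits the severity. It does not make the method fit the data: a descriptive 95% interval should still cover about 95%, and readers will look at zero.

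Two further points stand in part. Some of the over-coverage at 0.3% comes from rare-event discreteness, since Tango itself reaches 97.6%; at most the rest is due to MN. And an analysis of complete pairs drops anyone with only one period, for example a person who withdraws after an elevation at Injection 1. With about three expected events, one such loss would matter and need not be random. The loss is probably small, because the Evaluable Set removes whole participants and SAP 5.3 lists missing endpoint assessments as a possible major deviation, but it is a reason to keep the all-sample results alongside.

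Finally, the planned listing flags every elevated value, so a reader could build the paired table by hand. That supplies the counts but not an interval.

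**Conclusion.** The concern holds, as a point that should be fixed. For the three pooled comparisons, the planned interval ignores pairing that the protocol itself describes. It agrees with a paired interval when no elevation recurs and is too wide otherwise: on average 8% to 12% wider with a quarter of elevations recurring and 19% to 31% with half. Near the 0.3% planning rate this would not change whether zero is included; at higher counts with recurrence it can.

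This rests on two things that the documents do not give: the placebo exclusion rate (assumed 10%, hence the bound of 800) and the degree of recurrence (shown as a range). The direction is conservative. Point estimates, Clopper-Pearson intervals, the sample-size statement and single-day comparisons between sequences are not affected; on a single day each person is in one group only, and Miettinen-Nurminen is suitable.

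**What to change.** For the pooled visits only, overall and by subgroup:

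- Make a paired score interval (for example Tango), on participants with both samples, the main 95% interval for the difference.
- Show the paired 2x2 table: elevated on both, vaccine only, placebo only, neither.
- Keep Clopper-Pearson for each group's proportion on all evaluable samples, and Miettinen-Nurminen as a sensitivity analysis that retains one-period participants. State how many have one period only and how many of those are elevated.
- Keep Miettinen-Nurminen for single-day comparisons between sequences.
- Record the change in SAP 7.

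The cost is wording in SAP 6.3.1 and 7 and in Protocol 9.4.3, plus a few lines of code; no new data. A protocol amendment needs ethics approval (Protocol 10.1.1), though SAP 1 says the SAP prevails where methods differ. The change should be made before database lock and unblinding.

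The drawback is that the paired difference may not equal the difference of the displayed proportions. If 900 per group leave only 800 pairs and nothing recurs, the paired interval is about 6% wider (√(900/800) = 1.06).
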